6.5.2 Restricted Medications

The use of the following medications is restricted.

6.5.2.1 Visit 2 Through Visit 9

- Antipyretic, analgesic and anti-inflammatory agents, and antihistamines

 The concomitant use of these drugs is permitted if they have been used for treatment
 of a complication at Visit 2. However, the same dosage and administration should be
 maintained unless an AE has occurred, or the drug is judged to be no longer necessary
 due to remission of symptoms. Short-term concomitant use of these drugs for
 treatment of colds is also permitted. The use of local topical drugs is permitted. Shortterm is defined as 1 week in principle. If antipyretic, analgesic and anti-inflammatory
 agents or antihistamines that were not being used at informed consent are
 administered for > 2 weeks, or such administration is necessary, the trial will be
 discontinued according to the reason for discontinuation, "significant protocol
 deviation."
- Ultrashort-acting hypnotics and sedatives
 The concomitant use of ultrashort-acting hypnotics and sedatives (zolpidem, zopiclone, eszopiclone, triazolam) is permitted. However, the concomitant use is permitted with only 1 of these drugs and 2 or more of them must not be used concomitantly. The same dosage and administration should be maintained wherever possible.

6.5.3 Permitted Medications

All medications that are not specified as prohibited/restricted medications can be used concomitantly. However, the same dosage and administration should be maintained, and no new medications/therapies should be added wherever possible.

6.5.4 Rescue Medications

Not applicable.

6.5.5 Prohibited Therapies

The following therapies are prohibited so that the efficacy and safety of OPC-64005 can be appropriately assessed.

- Somatotherapies (electroconvulsive therapy, bright light therapy, sleep deprivation therapy, transcranial magnetic stimulation)
 - The concomitant use of these therapies is prohibited from Visit 1 through Visit 9.
- Psychotherapies (except for supportive psychotherapy generally conducted as part of routine medical practice)
 - The concomitant use of psychotherapies is prohibited from Visit 2 through Visit 9.

6.6 Intervention After the End of the Trial

Not applicable.

7 Stopping Rules, Withdrawal Criteria, and Procedures

7.1 Entire Trial or Treatment

If the sponsor terminates or suspends the trial for any reason, prompt notification will be given to the heads of the trial sites and regulatory authorities in accordance with regulatory requirements.

7.2 Individual Site

Individual trial site participation may be discontinued by the sponsor, investigator, or IRB if judged to be necessary for medical, safety, regulatory, ethical, or other reasons consistent with applicable laws, regulations, and GCP. The head of the trial site will notify the sponsor promptly if the trial is terminated by the investigator or the IRB of the trial site.

7.3 Individual Subject Discontinuation

7.3.1 Treatment Interruption

If drug eruption is suspected after IMP administration, IMP administration will be discontinued or interrupted (see Section 8.7.2.1).

7.3.2 Treatment Discontinuation

After treatment assignment, a subject may stop treatment permanently for a variety of reasons. Treatment discontinuations may be initiated by a subject who is not satisfied with treatment or may become medically necessary due to AEs, required treatment with a disallowed medication or therapy, or other issues, as determined by the investigator. However, each investigator must comprehensively review the circumstances and offer the subject options for continued treatment to the degree possible as described in Section 7.3.5.

If discontinuation of IMP administration occurs during the period between the start of IMP administration after Visit 2 and the start of IMP administration after Visit 9, the examination at discontinuation will be performed. If the subject refuses to undergo any examinations at the time of withdrawal, or if examinations cannot be performed due to an emergency or other circumstances, of the examination items specified for the time of withdrawal, only those items that can be performed will be performed.

If the specified examinations have been already performed on the day of discontinuation, they do not need to be repeated.

If discontinuation occurs during the period between the start of IMP administration after Visit 2 and the start of IMP administration after Visit 3, the post-treatment observation (Visit 11) is not necessary after the examination at discontinuation has been performed.

If discontinuation is decided during the period between the start of IMP administration after Visit 4 and the start of IMP administration after Visit 9, the IMP dose will be tapered (duration: 1 week [7 days \pm 2 days]) wherever possible after the examination at discontinuation has been performed (see Section 6.1.1.4). After the dose tapering, the subject will visit the trial site to undergo the same examination as scheduled at Visit 10, and the post-treatment observation (Visit 11) will be performed 2 weeks after the date of the final dosing.

If discontinuation occurs during the period between the start of IMP administration after Visit 3 and the start of IMP administration after Visit 4, dose tapering is not necessary after the examination at discontinuation has been performed, and the post-treatment observation (Visit 11) will be performed 2 weeks after the date of the final dosing.

If discontinuation of IMP administration occurs during the period between the start of IMP administration after Visit 9 and Visit 10, the examination at discontinuation is not necessary. The subject will visit the trial site to undergo the same examination as scheduled at Visit 10, and the post-treatment observation (Visit 11) will be performed 2 weeks after the date of the final dosing.

7.3.3 Documenting Reasons for Treatment Interruption or Discontinuation

A subject may discontinue the IMP for the reasons listed below:

- Adverse event
 - Subject decides to discontinue because of annoyance or discomfort due to a nonserious AE which is not otherwise determined to be an undue hazard
 - The investigator judges that the subject is at high risk for committing suicide based on his/her clinical symptoms, MADRS No. 10 "Suicidal Thoughts" score is ≥ 5, HAM-D Suicide (No. 11) score is ≥ 3, or "Yes" to Question 4 or Question 5 of the C-SSRS
 - Symptoms change to manic state
 - Continuing IMP places the subject at undue risk as determined by the investigator (eg, a safety concern that is possibly, probably, or likely related to IMP)
 - SAE
 - Occurrence of drug eruption
 - Other potentially IMP-related safety concerns or AEs
- Death
- Lost to follow-up
- Noncompliance with IMP (eg, drug compliance rate between the scheduled visits is < 65%)
- Physician decision
- Pregnancy (see Section 10.3)
- Significant protocol deviation
- Site terminated by sponsor
- Study terminated by sponsor
- Withdrawal by subject
- Lack of efficacy

If the subject discontinues IMP due to an AE, the investigator, or other trial personnel, will make every effort to follow the event until it has resolved or stabilized. Follow-up procedures in Section 7.3.1 and Section 7.3.2 must be followed.

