6.3 Measures to Minimize/Avoid Bias

This trial will be performed as a randomized double-blind trial to minimize bias.

Treatment assignment codes will not be disclosed to the subjects or investigator. Except for designated persons, the treatment assignment code will not be disclosed to the sponsor's trial staff including contract research organizations (CROs) (except for the bioanalytical laboratory and pharmacogenomic [PGx] laboratory) during the trial.

Emergency keys are controlled by the IRT system until the end of the trial. They will be disclosed according to the procedures for breaking the blind when a medical emergency occurs to a subject and it is judged important to identify the treatment assignment code for treatment of the subject. Procedures for breaking the blind can be found in Section 8.8.7.

If the IMP is collected by the sponsor before unblinding, the IMP will be collected in the sealed state.

Subjects will be assigned to the OPC-64005 10-mg group, OPC-64005 20-mg group, or placebo group at a ratio of 1:4:4 using the dynamic allocation method (minimization method). A separate specification will be developed to provide details.

Results of drug concentration measurement and PGx assessment should be retained in a manner that prevents their disclosure until unblinding at the end of the trial. These tests

will be performed by the specified laboratories, and will not be performed at a clinical laboratory of the trial site.

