7.4 Definition of Subjects Lost to Follow-up

Subjects who cannot be contacted before Visit 11, who do not have a known reason for discontinuation (eg, withdrew consent or AE), and for whom a survival status at the end of the trial cannot be determined will be classified as "lost to follow-up." Survival status can be determined from a variety of sources, either by obtaining acceptable documentation for death (ie, death certificate, medical records, public records, statement by a family member or primary care physician) or acceptable documentation for life (ie, direct contact with the subject, medical records, successful telephone contact with the subject, statement by a family member or primary care physician, or public records).

The site will make 3 documented attempts to contact the subject by telephone and in the event the site is unable to reach the subject by telephone, the site will attempt to contact the subject via certified mail or an alternative similar method, where appropriate, before assigning a "lost to follow-up" status.

If the subject was classified as "lost to follow-up", "Were you able to contact the subject?", "Date of contact/Date of final contact attempt" and "Contact method" will be recorded in source documents and eCRF.

8 Trial Procedures

The assessments to be conducted during the trial are summarized in Section 1.3.

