8.7.2.1 Dermatological Findings

Skin should be carefully observed. If drug eruption occurs after the start of IMP administration, administration of the IMP will be discontinued regardless of its severity, and the event will be reported as an immediately reportable event (IRE) after being assessed as drug eruption (see Section 8.8.3 and Section 8.8.5). The investigator will orally obtain consent from the subject and take pictures of the onset site of drug eruption wherever possible. The pictures (electronic data) will be kept as the source document, and the sponsor will collect copies of the pictures (electronic data). If necessary, the investigator will orally obtain consent from the subject and perform a drug-induced lymphocyte stimulation test (DLST). In addition, depending on the severity, the investigator will instruct the subject to see a dermatologist. If drug eruption is suspected, administration of the IMP will be interrupted, and when drug eruption has been ruled out, administration of the IMP can resume. However, the trial will be discontinued when the drug compliance rate between the scheduled visits is < 65%.

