9.1 Sample Size

As no clinical trials of OPC-64005 in patients with MDD have been previously conducted, the target number of subjects was determined based on the results from another antidepressant clinical trial using MADRS score as the primary endpoint. In the phase 3 clinical trial of escitalopram conducted outside Japan, 1 the mean change (\pm SE) from baseline in MADRS total score at the final timepoint of Week 8 (8 weeks after start of administration) determined using last observation carried forward analysis of covariance was -9.4 ± 0.9 in the placebo group (n = 119), -12.0 ± 0.9 in the citalogram 40-mg group (n = 125), -12.8 ± 0.8 in the escitalopram 10-mg group (n = 118), and -13.9 ± 0.8 in the escitalopram 20-mg group (n = 123). Referring to those results, in the present trial it is assumed that the difference between the OPC-64005 20-mg group and the placebo group in the change from baseline in MADRS total score at Week 6 of the double-blind treatment period will be -4 with a standard deviation of 11. To ensure a power of 80% in a two-sided test with a significance level of 0.05, 120 subjects each are required for the OPC-64005 20-mg group and the placebo group. For the OPC-64005 10-mg group, the number of subjects was set at 30 without statistical consideration. The planned number of subjects to be randomized for the trial was therefore set at 270.

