8.1.2 Sensitivity Analyses

8.1.2.1 Sensitivity Analysis for Handling of Missing Data

As a sensitivity analysis for handling of missing data, placebo multiple imputation and tipping point analysis on MNAR assumption will be performed using a pattern-mixture model with multiple imputation.

Multiple imputation analysis will be performed according to the following procedure. The number of imputations will be 100.

- 1) The Markov Chain Monte Carlo (MCMC) method will be used to impute intermittent missing data to produce a monotone missing data pattern.
- 2) The monotone regression method will be used to impute monotone missing data.
- 3) The same MMRM as that of the primary efficacy analysis will be used to analyze the multiple-imputed datasets.
- 4) The MIANALYZE procedure will be used to integrate the analysis results of the multiple-imputed datasets, and the estimate of the difference between the OPC-64005 20-mg group and the placebo group at Week 6 in the double-blind treatment period and its 95% CI and p-value will be determined.

In placebo multiple imputation, for discontinued subjects in each OPC-64005 group, MNAR will be assumed for missing data after discontinuation and an imputation model based on the placebo group will be used in imputation.

In tipping point analysis, for subjects in each OPC-64005 group who discontinued treatment for any of the following reasons, MNAR will be assumed for missing data after discontinuation.

- Withdrawal for any reason
- Withdrawal due to AEs, a lack of efficacy, or consent withdrawal
- Withdrawal due to AEs or a lack of efficacy

For subjects in each OPC-64005 group who discontinued treatment for reasons assumed as MNAR, the MAR assumption will be used to impute post-discontinuation missing data, add Δ (intergroup differences in MMRM of the primary efficacy analysis) \times k% to the imputed value, and increase k until a statistically significant conclusion is reversed ($p > 0.05$).

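### Some discontinuation reasons can be misclassified under the Protocol's coding rules, which affects the disposition table and two of the three tipping-point sets

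*Protocol*

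**What the plan says.** **Restricted drugs (Protocol 6.5.2.1).** A subject who takes, or needs, an antipyretic, analgesic, anti-inflammatory agent or antihistamine for more than 2 weeks, and was not using it at consent, is to be "discontinued according to the reason for discontinuation", and the reason named is *significant protocol deviation*. There is no exception for a drug that treats an AE. The same bullet does make an AE exception for changing the dose of a drug already in use.

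**Suspected drug eruption (Protocol 8.7.2.1).** IMP is interrupted on suspicion and may resume once eruption is ruled out. However, "the trial will be discontinued when the drug compliance rate between the scheduled visits is < 65" per cent. Section 6.1.1.6 refers a stop below 65% to 7.3.3, where one listed reason is "Noncompliance with IMP (eg, drug compliance rate between the scheduled visits is < 65" per cent. The same list contains *Adverse event*, with sub-items for confirmed drug eruption and for other potentially IMP-related safety concerns. Nothing says which reason prevails when two apply, and there is no residual *Other* item.

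**Lost to follow-up (Protocol 7.4).** Three conditions must hold together: no contact before Visit 11, no known reason, and undetermined survival. It is subjects "for whom a survival status at the end of the trial cannot be determined will be classified as" lost to follow-up. Survival may be established from a relative, a physician or public records.

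**Where the reasons are used.** SAP 7.1 tabulates double-blind discontinuations by reason. SAP 8.1.2.1 runs the tipping-point analysis on three sets of OPC-64005 dropouts: any reason (set 1); AEs, lack of efficacy or consent withdrawal (set 2); and "Withdrawal due to AEs or a lack of efficacy" (set 3).

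**The concern.** The recorded reason should describe why the subject stopped. In these places it may describe only the rule that was triggered. A subject whose AE needed prolonged analgesia is filed as a protocol deviation. A subject who paused IMP on instruction may be filed as noncompliant. A no-show known to be alive has no label that describes what happened.

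In sets 2 and 3, a dropout with an included reason is imputed under MNAR and receives the k-scaled shift, while any other dropout stays at MAR with no shift. An AE-driven stop filed elsewhere therefore escapes the shift, and the two sets look more robust than they are. The disposition table would also understate AE withdrawals. It could disagree with the SAP 9.2 table of TEAEs leading to IMP discontinuation, because Protocol 8.8.2 records the action taken with IMP for each AE separately.

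**Working it through.** **1. The plan's own figure.** Protocol 9.1 assumes a difference that "will be -4 with a standard deviation of 11", and states: "To ensure a power of 80% in a two-sided test with a significance level of 0.05, 120 subjects each are" required. The normal formula gives n = 2 × (1.960 + 0.842)² × 11² / 4² = 118.7, so 119 per arm. At 120 per arm, power is 80.4% (normal) or 80.1% (noncentral t). The figure of 120 reproduces, and these inputs are reused in step 4.

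**2. When a pause triggers the compliance stop.** Section 6.1.1.6 defines compliance as tablets taken / (prescription days × 2). This check assumes that paused days stay in the denominator, as 8.7.2.1 implies.
- 7-day interval, 2 days paused: 10/14 = 71.4%, no stop.
- 7-day interval, 3 days paused: 8/14 = 57.1%, stop.
- The trigger is 2 days in intervals of 4–5 days, 3 days in intervals of 6–8 days, and 4 days in intervals of 9–11 days.

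**3. How often the routes might arise.** Protocol 2.3 gives only rates of any occurrence.
- Headache: 24/313 and 6/77, about 9 per 120.
- Rash: 5/313 and 2/77, about 2 to 3 per 120.

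The documents give no rate for headache needing a new drug for more than 2 weeks, or for a suspected eruption paused long enough to breach 65%. The number misfiled cannot be derived from them.

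**4. Illustration for set 3.** Assumptions: the planning effect is observed exactly; complete-data variance (no extra multiple-imputation variance); a shift unfavourable to the 20-mg arm; 28 AE stops in that arm (18/77 = 23.4% in the earlier AD/HD trial, Protocol 4.3.2, × 120); no lack-of-efficacy stops; 3 to 6 AE stops misfiled.
- SE = 11 × √(2/120) = 1.420.
- Headroom = 4 − 1.970 × 1.420 = 1.202.
- Tipping k = 1.202 / (4 × n/120), where n is the number in the set.

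| AE stops retained in set 3 | k with no lack-of-efficacy stops | k with 10 lack-of-efficacy stops added (assumed) |
|---|---|---|
| 28 (none misfiled) | 129% | 95% |
| 25 (3 misfiled) | 144% | 103% |
| 22 (6 misfiled) | 164% | 113% |

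The relative rise in k is 28/25 to 28/22, or 12% to 27%. With 10 lack-of-efficacy stops it is 38/35 to 38/32, or 9% to 19%. At k = 100% the lost penalty is 4 × 3/120 = 0.10 to 4 × 6/120 = 0.20 MADRS points. With only 10 AE stops and no others, k starts at 1.202 / (4 × 10/120) = 361%.

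**5. Which analyses depend on the reason.**
- Primary MMRM: no.
- Placebo multiple imputation: no; it covers all discontinued OPC-64005 subjects.
- Set 1: no.
- Sets 2 and 3: yes, through AE-driven stops filed elsewhere.
- Lost-to-follow-up wording: lost to follow-up is in neither set 2 nor set 3. Set 2 changes only if the no-show is coded as withdrawal by subject and that is read as consent withdrawal. This adds a penalised subject, which is the conservative direction.

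**The case against.** A reader might infer that the Protocol forces the wrong reason throughout. It does not. For the compliance route, 7.3.3 lists reasons for which a subject may stop, the 65% figure is only an example, 8.7.2.1 names no code, and *Adverse event* stays available. Confirmed eruption is expressly listed there. That route is an ambiguity.

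The restricted-drug rule can also be defended. Section 7.3.2 treats AEs and required treatment with a disallowed medication as separate grounds, and a subject who tolerates IMP but breaches the medication rule is not self-evidently an AE withdrawal. Coding every such case as an AE could overcount. This stands, and it is why the fix relies on the investigator's attribution. It does not remove the gap: when the AE is the cause, the text still prescribes the other code.

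The plan has its own protection. Set 1 and placebo multiple imputation take in every OPC-64005 dropout whatever the code, and AE-related discontinuation of IMP is tabulated separately. This also stands, and it limits the harm to two scenarios and one table in an exploratory phase 2 trial.

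Finally, the illustration rests on assumptions. The 28 comes from a trial that started at a higher dose, and Protocol 4.3.2 says the starting dose here was lowered because of those early stops. It could also be said that every k from 129% to 164% exceeds 100%, so the reading would not change. That holds only with no lack-of-efficacy stops: with 10, k moves from 95% to 103%–113%. The SAP gives 100% no special status in any case.

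**Conclusion.** The point holds as a risk of misclassification. Read literally, two rules put stops under a reason that is not the cause, or leave them without one: the fixed code in 6.5.2.1 and the survival condition in 7.4. The link between 6.1.1.6, 7.3.3 and 8.7.2.1 leaves a third case undecided. The consequences are a disposition table that can mislabel stops and tipping-point sets 2 and 3 that can look somewhat more robust. The 7.4 wording does not contribute to that apparent robustness; it affects the disposition label and, at most, set 2 in the conservative direction.

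The documents do not support saying that the disposition table and tipping-point sets are wrong, or that robustness is overstated by a known amount. The number misfiled is unknown, and the eruption route is probably small. The move from about 129% to 144%–164% is an illustration under the assumptions listed, and it shrinks proportionally once lack-of-efficacy stops are counted. The primary result does not depend on this point.

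**What to change.** Leave every stopping rule as it is and change only the coding, before unblinding, since later recoding would be open to challenge.

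- **Protocol 6.1.1.6, 6.5.2.1, 7.3.3 and 8.7.2.1:** reconcile these so that the eCRF records the underlying cause separately from the rule that triggered the stop. The reason is *Adverse event* when the investigator attributes the stop to an AE, including an AE that required the restricted drug or a suspected AE for which IMP was withheld. The noncompliance and deviation codes remain for stops without such a cause.
- **Protocol 7.4:** classify as lost to follow-up when the documented contact attempts fail and no reason is known, and record survival status as a separate item.
- **SAP 7.1 and 8.1.2.1:** tabulate disposition and define sets 2 and 3 by the underlying cause, with an explicit mapping from each eCRF reason. The SAP's consent withdrawal has no identically named item in 7.3.3, which uses *Withdrawal by subject*.

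The cost is a few words in each section, one eCRF item and completion guidance. The reported AE withdrawal rate may be slightly higher, and the tipping points in sets 2 and 3 slightly less favourable. Some judgement by the investigator remains.
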